Appendix 2. STATISTICAL METHODOLOGY DETAILS

Appendix 2.1. Sample SAS Code for Cox Proportional Hazards Model - Time-to-death Endpoint

Sample SAS (SAS Institute Inc.) code to fit the Cox proportional hazard model specified in [Section 8.1](#) is given below:

```
proc phreg data= input dataset (where=(trtxn in ("treatment1" "treatment2")));  
  class trtxn cohort;  
  model Time_to*censor(1)=trtxn ;  
  contrast 'treatment2 vs. treatment1' trtxn -1 1(values) / estimate=keyword (e.g.  
  exp=exponentiates the contrast that is to be estimated) alpha=0.05;  
run;
```

Where,

TX=treatment group

TIME_TO=time to death (survival days)

COHORT= stratification variable (all or by strata)

CENSOR=censoring variable, 1=censored, 0=event

Where the variable 'STRATA' has the following 4 levels:

- PAH-treatment naïve at study entry and disease etiology of idiopathic;
- PAH-treatment naïve at study entry and disease etiology of CTD/surgical repair;
- On PAH-treatment at study entry and disease etiology of idiopathic;
- On PAH-treatment at study entry and disease etiology of CTD/surgical repair.

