With the estimated recruitment rate, the study is expected to complete enrollment in about 4.3 years with a total duration of about 7.7 years to reach the required number of events (143 deaths).

Statistical Analysis for Primary Endpoint

The primary efficacy analysis will be conducted using the intent-to-treat (ITT) population. All events occurring up until the end of the trial, including events observed from discontinued patients, will be included in the primary efficacy analysis. The efficacy analyses will also be conducted using the per-protocol (PP) population as sensitivity analyses.

Treatment comparison will be conducted using Cox proportional hazard regression model stratified by PAH treatment at entry of the study (PAH-treatment naïve vs. on PAH treatment) and etiology of PAH (idiopathic vs. secondary to CTD/surgical repair). If the 1-sided upper confidence limit of the hazard ratio (80 mg TID/5 mg TID) is less than 2, then the null hypothesis that the mortality rate in the 80 mg is worse than double the rate in 5 mg will be rejected. In the event that the hazard ratio is statistically significantly less than 1, then superiority of 80 mg TID over 5 mg TID will be claimed.

Pharmacokinetic and Pharmacokinetic-Pharmacodynamic Methods

Not applicable for this study.

SCHEDULE OF ACTIVITIES

The Schedule of Activities table provides an overview of the protocol visits and procedures. Refer to STUDY PROCEDURES and ASSESSMENTS sections of the protocol for detailed information on each procedure and assessment required for compliance with the protocol.

The investigator may schedule visits (unplanned visits) in addition to those listed on the schedule of activities, in order to conduct evaluations or assessments required to protect the wellbeing of the subject.

Protocol Activity	Screen	Day 1	Wk 2	Mo 3, 9	Mo 6, 12, 18, 24, 30, 36, 42, 48, 54, 60, 66, 72, 78, 84, 90, 96 followed by every 6 months until the end of study treatment	Mo 15, 21, 27, 33, 39, 45, 51, 57, 63, 69, 75, 81, 87, 93, 99 followed by every 6 months until end of study treatment ^h	End of Treat- ment	Follow- Up Check (28 days)
Visit Window	Day -21 to Day -1		± 3 days	±10 days	±10 days	±10 days	± 7 days	± 7 days
Informed consent	X							
Inclusion/Exclusion Criteria	X	X						
Randomization		X						
Demography (including ethnicity, race, weight, height, smoking & alcohol classification)	X							
Primary Diagnosis	X							
Medical History (including drug allergies)	X							

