9.2. Efficacy Analysis

9.2.1. Analysis of Primary Endpoint

The primary efficacy analysis will be conducted using the intent-to-treat (ITT) population. All events occurring up until the end of the trial, including events observed from discontinued patients, will be included in the primary efficacy analysis. The efficacy analyses will also be conducted using the per-protocol (PP) population as sensitivity analyses.

Treatment comparison will be conducted using Cox proportional hazard regression model stratified by PAH treatment at entry of the study (PAH-treatment naïve vs. on PAH treatment) and etiology of PAH (idiopathic vs. secondary to CTD/surgical repair). If the 1 sided upper confidence limit of the hazard ratio (80 mg TID/5 mg TID) is less than 2, then the null hypothesis that the mortality rate in the 80 mg TID is worse than double the rate in

5 mg TID will be rejected. In case that the hazard ratio is statistically significantly less than 1, then superiority of 80 mg TID over 5 mg TID will be claimed. Treatment comparison will also be evaluated using the exact test as sensitivity analysis.

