5.5. Randomization Stratification Misallocations

- Randomized as PAH Treatment Naïve but should have been randomized as On PAH Treatment.
- Randomized as On PAH Treatment but should have been randomized as PAH Treatment Naïve.

Classification of a patient into these stratum will be done programmatically and is presented on [Appendix 1](#).

Subjects will be put in the stratum that reflects clinical reality and will be analyzed under the correct determined stratum, ie, stratum determined by clinical data that they should have been randomized. A data listing will be provided for subjects with randomization stratification error.

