6.3. Covariates

The analyses of the primary and secondary endpoints will be performed using the following two randomization stratification factors as covariates:

- PAH treatment at entry (PAH-treatment naïve vs. on PAH-treatment);
- Etiology of PAH (idiopathic vs. secondary to CTD/surgical repair).

The analyses of 6MWD will also include baseline results as a covariate.

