8. STATISTICAL METHODOLOGY AND STATISTICAL ANALYSES

8.1. Primary Efficacy Analyses

For time to death, treatment comparison will be conducted using Cox proportional hazard regression model.^{4,5} The estimate of the hazard ratio for treatment (sildenafil 80 mg TID/5 mg TID, 80 mg/20 mg TID, and 20 mg TID/5 mg TID) together with its confidence interval (CI) and p-value will be provided. Significance level will be determined using the O'Brien-Fleming approach at each interim analysis and the final analysis. The overall significance level is set at 2.5% (1-sided).

The Cox proportional hazard regression model described above will be conducted using PP population as sensitivity analysis.

Time to death analysis will be conducted by PAH treatment at entry of the study (PAH-treatment naïve vs. on PAH treatment) and etiology of PAH (idiopathic vs. secondary to CTD/surgical repair) based on ITT population and PP population.

The duration of overall survival will be summarized graphically using Kaplan-Meier plots for each of the treatment group. Tabular summaries of the Kaplan-Meier curves giving the median, quartiles, mean, standard error of the mean and range of overall survival will also be provided for each treatment group. Number of events and survival rate at each year will also be tabulated by treatment groups where on-treatment deaths are defined as deaths ≤ 7 days post last study dose.

Analyses will be done based on ITT and PP population. Similar analyses will also be conducted for each level of randomization stratification factors.

For treatment comparison, the exact Logrank test will be conducted as sensitivity analysis using ITT and PP populations.

As described in [Section 4.1](#), time to death secondary analyses will be conducted for treatment comparisons for 80 mg vs. 20 mg, and 20 mg vs. 5 mg. All above analyses/methods will be performed for these two treatment comparisons and are considered secondary analyses of the primary efficacy endpoint (time-to-death).

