8.2. Efficacy Analyses for Secondary and Tertiary Endpoints

There will be no p-value adjustment for secondary and tertiary data analyses.

A. Time to First Event of Clinical Worsening

Cox proportional hazard model, analyses using Kaplan-Meier method described above will be used for time to first event of clinical worsening. The analyses will be done using ITT population and PP population for overall subjects and by randomization stratification factors.

In addition, a summary table will be presented showing n(%) of subjects with first qualifying clinical worsening event by event (none, all-cause mortality, non-elective hospital stay for worsening PAH or disease progression) for each study treatment group using ITT and PP population for overall subjects and by randomization stratification factors.

Sensitivity analysis for the secondary endpoint time to first event of clinical worsening will be performed for adjudicated clinical worsening events. All the above described analysis will be conducted.

B. 6MWD

For change from baseline, descriptive summaries (n, mean, SD, 95% CI of the mean, median, and range) will be tabulated at each study visit for each treatment group using ITT and PP population for overall subjects and by randomization stratification factors.

Percent of subjects in each category of 6MWD and change will be tabulated at each study visit for each treatment group using ITT and PP population for overall subjects and by randomization stratification factors. The 95% CI of the percentage will also be tabulated (except for the category of 'missing').

For change from baseline at Month 6 and Month 12, treatment comparisons will be conducted using MMRM with covariates of baseline value, treatment and randomization stratification factors. Least square mean difference, its 95% CI and p-value will be tabulated for each treatment comparison (sildenafil 80 mg TID vs. 5 mg TID, 80 mg TID vs. 20 mg TID and 20 mg TID vs. 5 mg TID).

Analyses will be done based on ITT and PP populations for overall subjects and subgroups by randomization stratification factors.

Figures will be provided for the least square mean change from baseline and 95% CI at Month 12 for each study treatment group for ITT population and PP population for overall subjects and by randomization stratification factors.

C. BORG Score

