Appendix 2.3. Sample StatXact Code for Exact Logrank Test - Time-to-death Endpoint

The following StatXact (Cytel Inc.) codes can be used for statistical analysis of time to death (overall survival):

```
PROC TWOSAMPL DATA=;  
  LO/EX;  
  PO TX;  
  RE TIME_TO;  
  CE CENSOR;  
  STRATUM STRATA;  
RUN;
```

Where the variable 'STRATA' has the following 4 levels:

- PAH-treatment naïve at study entry and disease etiology of idiopathic;
- PAH-treatment naïve at study entry and disease etiology of CTD/surgical repair;
- On PAH-treatment at study entry and disease etiology of idiopathic;
- On PAH-treatment at study entry and disease etiology of CTD/surgical repair.

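### The primary Cox model is stratified in the protocol, covariate-adjusted in SAP 6.3, unspecified in SAP 8.1, and fitted on treatment alone in the SAP sample code

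*SAP*

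**What the plan says.** - Protocol 9.2.1: "Treatment comparison will be conducted using Cox proportional hazard regression model stratified by PAH treatment at entry of the study", with etiology of PAH as the second factor. The synopsis agrees: "Cox proportional hazard regression model stratified by PAH treatment at entry of the study".
- SAP 6.3: "The analyses of the primary and secondary endpoints will be performed using the following two randomization stratification factors as covariates".
- SAP 8.1: "For time to death, treatment comparison will be conducted using Cox proportional hazard regression model". It mentions neither strata nor covariates for this model.
- SAP Appendix 2.1, offered as code for the 8.1 model: "model Time_to*censor(1)=trtxn". There is no `STRATA` statement. `COHORT` appears only in `CLASS`, where it has no effect on the fit. A four-level variable named `STRATA` is defined below the code and never used.
- SAP Appendix 2.3, the exact log-rank sensitivity test, does use the four strata: "STRATUM STRATA".
- SAP 8.2 carries the Cox model over to the first secondary endpoint: "Cox proportional hazard model, analyses using Kaplan-Meier method described above will be used for time to first event of clinical worsening".
- SAP 5.5 sets a rule for wrongly assigned strata: "Subjects will be put in the stratum that reflects clinical reality and will be analyzed under the correct determined stratum".

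**The concern.** A confirmatory mortality test needs one model, fixed before unblinding and matched to the stratified randomisation. Here the protocol and SAP allow three readings, and the only one written out as code is the one that ignores the strata. The stratum-correction rule in SAP 5.5 would have no effect on that fit.

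The direction of the error matters. Leaving prognostic factors out of a Cox model pulls the estimated HR toward 1. If the true HR (80 mg over 5 mg) is near the margin of 2, the pull favours non-inferiority. If it is below 1, the estimate moves up and the superiority claim in SAP 4.2 becomes harder to reach. At exactly 1 there is no pull. Protocol section 9 also requires a major change to the primary analysis to appear in a protocol amendment, and the current protocol still says stratified.

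**Working it through.** **The texts side by side**

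| Place | Role of the two factors |
|---|---|
| Protocol synopsis, 9.2.1 | Strata: a separate baseline hazard in each of 2 × 2 = 4 cells |
| SAP 6.3 | Covariates: one baseline hazard, two regression terms |
| SAP 8.1 | Not stated |
| SAP Appendix 2.1 | Not in the fit |

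The other treatment-comparison code for efficacy endpoints carries the factors: exact log-rank (Appendix 2.3), MMRM (2.4) and stratified Wilcoxon (2.6, which has a `strata cohort` line). Only the Cox code lacks them.

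**The plan's own figure.** Freedman's formula for margin 2, one-sided 0.025 and 90% power gives ((2+1)/(2−1))² × (1.960 + 1.282)² = 9 × 10.51 = 94.6, so 95 deaths in two arms. Over three arms, 95 × 1.5 = 142.5, so 143. At 143 × 2/3 = 95.3 two-arm deaths, the stated efficacy and futility bounds give 90.2% power. The 143 reproduces, and the choice of model text does not change it.

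**Simulation inputs from the documents**
- 143 per arm; accrual 429/100 = 4.29 years.
- 15% mortality at 2 years in the 5 mg arm: −ln(0.85)/2 = 0.081 per year.
- 20% dropout, taken as spread over 7.7 years: −ln(0.8)/7.7 = 0.029 per year.
- Final bound p < 0.022 (z = 2.014); interim bound p < 0.0015 (z = 2.968).

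**Assumed inputs**
- Deaths split evenly over arms: 143 × 2/3 ≈ 95 and 72 × 2/3 = 48 in the two compared arms.
- Factor HRs from 1 to 3.
- 35% secondary etiology and 50% on PAH treatment, later varied.

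Non-inferiority is declared when ln(HR) + z × SE < ln 2. Each look is tested on its own.

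**Final look, true HR 2: false non-inferiority** (20,000 runs, Monte Carlo error about 0.1 point)

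| Factor HRs (etiology, PAH treatment) | Treatment only | Stratified | Covariates |
|---|---|---|---|
| 1, 1 | 2.50% | 2.46% | 2.46% |
| 1.5, 1.5 | 2.44% | 2.30% | 2.20% |
| 2, 2 | 2.81% | 2.31% | 2.31% |
| 3, 2 | 3.55% | 2.46% | 2.49% |
| 3, 3 | 4.10% | 2.46% | 2.40% |

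The mean treatment-only HR falls from 2.01 to 1.85 across these rows. With 20% or 50% secondary etiology and 30 to 70% on PAH treatment, factor HRs 2,2 and 3,2 give 2.8 to 3.3% treatment-only and 2.2 to 2.4% stratified.

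A separate simulation used four equal strata, no dropout, a single test at 0.025 and 4,000 trials per scenario (Monte Carlo error about 0.25 point). It shows the same direction. For both factor HRs at 1, 1.5, 2 and 3, treatment-only gives 2.7, 2.9, 3.1 and 3.8%; stratified stays between 2.5 and 2.7%.

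**Other true values at the final look**
- HR 1 (5,000 runs): mean estimate 1.00 in every model; power 91.8 to 92.4% treatment-only, 90.4% stratified.
- HR 0.5 (5,000 runs): mean estimate 0.52 to 0.53 treatment-only, 0.50 stratified.
- HR 0.6, factor HRs 3,2 (6,000 runs): superiority claimed in 59% treatment-only, 66% stratified.

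**Interim look, true HR 2** (48 deaths, 30,000 runs): 0.14 to 0.21% treatment-only, 0.12 to 0.21% stratified. With SE ≈ √(4/48) = 0.289, crossing needs an observed HR below about 2 × exp(−2.968 × 0.289) = 0.85.

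**The case against.** The strongest reply is that this is one missing line in a template. The block contains placeholders and would not execute as printed. It names `COHORT` a stratification variable and lists the four strata, so a dropped `STRATA` line is the natural reading. The protocol controls the primary analysis and is clear. SAP 8.1 is silent rather than unadjusted, and read with 6.3 it is adjusted. SAP 8.1 also has a sentence running time to death by the two factors, which resembles the protocol's stratification clause. Finally, the inflation is computed at a final look the trial never reached, at a true HR of 2 that sits poorly with the DMC's concern about mortality on 5 mg, and with assumed factor HRs.

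Much of this stands. The code may simply be incomplete, and nothing shows that an unadjusted model was run. Strata against covariates is immaterial. The inflation is conditional, and the interim error rates do not differ visibly.

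Three parts do not stand. First, the SAP never says the Cox model is stratified, so its text does not repair its code. Second, the sentence in 8.1 matches the subgroup runs that the table in SAP 8.3 lists by randomisation factor. Third, similar average error rates at the interim do not make the models interchangeable in a single trial: in simulation at that bound (true HR 1 or 0.7, factor HRs 2 to 3) the treatment-only and stratified fits disagreed on crossing in about 4 to 5% of trials. That does not suggest the stopping decision was wrong. It is a reason to record which model produced it.

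**Conclusion.** The concern holds. The primary model is specified inconsistently, and the printed code contradicts the protocol and ignores the randomisation strata. This should be fixed, but it does not undermine the trial.

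The practical gap is between the treatment-only fit and the other two. At the final look with a true HR of 2, treatment-only raises false non-inferiority by about 0.5 point at factor HRs 2,2 (2.81 − 2.31) and about 1.6 points at 3,3 (4.10 − 2.46). At 1.5 or less the gap is within about 0.25 point. On the other side of 1 it costs about 7 points of superiority power (66 − 59) at a true HR of 0.6 with factor HRs 3,2. These sizes rest on assumed factor HRs and stratum mixes, an even split of deaths over arms, and single-look tests. They do not give the overall type I error of the sequential design. The inconsistency in the text depends on none of these assumptions.

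**What to change.** - Appendix 2.1: add a `STRATA` statement with the four-level variable, using the corrected stratum from SAP 5.5.
- SAP 8.1: state that the Cox model is stratified by PAH treatment at entry and etiology. SAP 8.2: say the same for time to clinical worsening.
- SAP 6.3: make the two factors strata for time-to-event endpoints and covariates for 6MWD.
- Label any treatment-only fit as a sensitivity analysis.
- SAP 9: state which model was used for the 72-death interim.

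The cost is one line of code and a few sentences before database lock. No extra deaths are needed. At a true HR of 1, stratifying gives up 91.8 − 90.4 = 1.4 to 92.4 − 90.4 = 2.0 points of power relative to the treatment-only fit and still delivers about 90%. If lock has passed, report the stratified result as primary and describe the discrepancy in the study report, where SAP section 2 already places deviations from the plan.

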Appendix 2.2. Sample SAS Code for KM Plots (LIFETEST) - Time-to-death Endpoint

The following SAS codes can be used for Kaplan-Meier plots/analysis:

```
PROC LIFETEST;  
  TIME TIME_TO*CENSOR(1);  
  STRATA TX;  
RUN;
```

Where,

TX=treatment group

TIME_TO=time to death (survival days)

CENSOR=censoring variable, 1=censored, 0=event

Appendix 2.3. Sample StatXact Code for Exact Logrank Test - Time-to-death Endpoint

The following StatXact (Cytel Inc.) codes can be used for statistical analysis of time to death (overall survival):

```
PROC TWOSAMPL DATA=;  
  LO/EX;  
  PO TX;  
  RE TIME_TO;  
  CE CENSOR;  
  STRATUM STRATA;  
RUN;
```

Where the variable 'STRATA' has the following 4 levels:

- PAH-treatment naïve at study entry and disease etiology of idiopathic;
- PAH-treatment naïve at study entry and disease etiology of CTD/surgical repair;
- On PAH-treatment at study entry and disease etiology of idiopathic;
- On PAH-treatment at study entry and disease etiology of CTD/surgical repair.

Appendix 2.4. Sample SAS Code for MMRM Analyses - 6MWD Endpoint

Sample SAS code to fit the MMRM model specified in 8.1 is given below. The response variable Chg is change from baseline at Month 12, trtxn is treatment group, prev_tx = pah treatment at entry (pah-treatment naïve or on pah treatment) and etiology = etiology (idiopathic or secondary to CTD/surgical repair). The following SAS codes can be used for statistical analysis:

```
PROC MIXED data= input dataset;  
  CLASS trtxn PREV_TX ETIOLOGY usubjid avisitn;  
  MODEL chg = BASE trtxn PREV_TX ETIOLOGY avisitn trtxn*avisitn/solution;  
  REPEATED avisitn/TYPE=UN SUBJECT=usubjid(trt_n);  
  LSMEANS trtxn*avisitn/PDIFF TDIFF alpha=0.05 diff=control ('1' '4');  
  LSMEANS trtxn*avisitn/PDIFF TDIFF alpha=0.05 diff=control ('2' '4');  
  ods output lsmeans=lsmeansop diffs=trtcmp;  
RUN;
```

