2.2. Endpoints

This study will use an independent endpoint adjudication committee to determine whether certain investigator-reported events meet the definition of disease-related efficacy endpoints, using pre-defined endpoint criteria.

For those serious adverse events (SAEs) that are handled as disease related efficacy endpoints (which may include death), a data monitoring committee (DMC) will conduct unblinded reviews on a regular basis throughout the trial (see Data Monitoring Committee Section).

Any SAE that is adjudicated by the endpoint adjudication committee NOT to meet endpoint criteria is reported back to the investigator site of incidence; the investigator at the study site must evaluate and report that SAE to Pfizer, in accordance with the time frames described in the Serious Adverse Event Reporting Requirements section of this protocol. The investigator's SAE awareness date in this instance is identified as the date on which the investigator site of incidence receives the nonendpoint SAE back from the endpoint adjudication committee. Handling these SAEs in this manner will allow Pfizer to meet its sponsor reporting obligations to regulatory authorities upon receipt of such SAEs.

However, when the investigator has judged the SAE to have a causal relationship with the investigational product, the investigator must additionally report the event to the sponsor as described in the Serious Adverse Event Reporting Requirements section, even if that event is a component of the endpoint.

Any events that remain unadjudicated at the annual safety report cutoff date will not be included in the safety tables of the report.

Primary Efficacy Endpoint:

- Time to death (Mortality).

Secondary Efficacy Endpoints:

- Time to first event (Clinical Worsening); and
- 6MWD at Months 6 and 12.

Clinical worsening⁸ for the purpose of this study is defined as:

- All-cause mortality;
- Hospital stay for worsening PAH (including but not limited to right heart failure [RHF], initiation of prostanoids, lung transplantation, or septostomy); or

- Disease progression (defined as a reduction from baseline in the 6MWD test by at least 15% and worsening functional class from baseline, both confirmed by a 2nd test/evaluation within 2 weeks (cannot be performed on same day). Patients with functional class IV at baseline only need to meet the 6MWD criteria as they cannot have deterioration in functional class. The date of the event will be the first date of the two 6MWTs.

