9.2.2. Analysis of Secondary Endpoints

For continuous endpoints, analysis of covariance (ANCOVA) or analysis of variance (ANOVA) will be used. Estimated mean differences between treatments (80 mg TID vs. 5 mg TID, 80 mg TID vs. 20 mg TID, 20 mg TID vs. 5 mg TID) and their respective 95% CI and p-values will be calculated.

For categorical endpoints, treatment comparison will be conducted using Chi-square test or Fisher's exact test, whichever is appropriated. Differences in rate and its 95% CI and p-value will be calculated for each treatment comparison (80 mg TID vs. 5 mg TID, 80 mg TID vs. 20 mg TID, 20 mg TID vs. 5 mg TID).

For time-to-event endpoints, similar analyses as used for primary endpoint will be used.

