7. HANDLING OF MISSING VALUES

Missing data will not be imputed. For 6MWD at Month 6 and 12, mixed model for repeated measure method (MMRM) will be used for statistical analyses for treatment comparisons. For MMRM, all available data in Month 6 and 12 will be included in the analyses and any missing data are assumed missing at random. Details of the analyses are described in [Section 8](#).

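### The sample repeated-measures code for 6MWD uses one baseline slope for Months 6 and 12; adding `BASE*avisitn` is a minor, nearly free safeguard that matters only if the true slopes differ

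*SAP*

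**What the plan says.** The Protocol (Section 2.2) names "6MWD at Months 6 and 12" as a secondary endpoint. For continuous secondary endpoints, Protocol Section 9.2.2 says "analysis of covariance (ANCOVA) or analysis of variance (ANOVA) will be used".

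The SAP uses a mixed model for repeated measures (MMRM) instead. Section 8.2 B says "treatment comparisons will be conducted using MMRM with covariates of baseline value, treatment and randomization stratification factors". Section 6.3 adds only this on baseline: "The analyses of 6MWD will also include baseline results as a covariate". Section 7 rules out imputation and states that "all available data in Month 6 and 12 will be included in the analyses and any missing data are assumed missing at random".

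The only full model statement is the sample code in Appendix 2.4: "MODEL chg = BASE trtxn PREV_TX ETIOLOGY avisitn trtxn*avisitn/solution", with "REPEATED avisitn/TYPE=UN" for the covariance. It is introduced permissively: "The following SAS codes can be used for statistical analysis". Baseline appears once, as a main effect, and no other section asks for a baseline effect by visit.

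**The concern.** The code lets the dose effect differ by visit and leaves the covariance unstructured, yet holds the baseline slope equal at the two visits. An ANCOVA fitted at Month 12 alone, which the Protocol wording would allow, has its own slope. The MMRM code adds a restriction without giving a reason.

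Unequal slopes are possible. The Month 6 window in SAP Appendix 3.1 runs from Day 2 to Day 274, so an early walk can count as Month 6 and may track baseline more closely than a Month 12 walk. Missing Month 12 walks are also built into the design: after stopping treatment, a subject has one End of Treatment walk and then survival contacts only. Missing-at-random inference relies on the mean model being right in baseline.

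This MMRM is the only between-dose inference the SAP specifies for 6MWD, so a wrong slope would pass straight into the reported difference, interval and p-value.

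**Working it through.** **Stated figure.** The documents give no power, SE or sample size for 6MWD, so there is nothing to reproduce.

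**Inputs from the documents.** 143 subjects per arm and 20% overall drop-out (Protocol 9.1). SD of 6MWD change 60.950 and 57.557 m at Week 12 in the earlier bosentan add-on study (Protocol 1.1).

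**Assumptions not in the documents.** True dose difference 0; residual SD 60 m; Month 6/Month 12 correlation 0.7; baseline SD 80 or 100 m; slope gaps of 0.1, 0.2 and 0.3 m per m. Moderate missingness: in the 5 mg arm 30% of low-baseline and 10% of high-baseline subjects, against 20% throughout in the 80 mg arm. Strong missingness: 50% and 10%, against 10%.

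**Where a slope gap comes from.** For a change score, the slope at visit t is corr(baseline, visit t) × SD_t/SD_0 − 1. With equal SDs, correlations of 0.85 and 0.65 give −0.15 and −0.35, a gap of 0.2.

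**Bias by hand.** Take low and high baseline as the two halves of a normal distribution, with means ∓0.798 SD. Let the same subjects miss both walks. Under moderate missingness the observed 5 mg subjects have mean baseline (0.9 − 0.7) × 0.798/(0.9 + 0.7) = 0.0997 SD above the 80 mg arm, which is 8.0 m at SD 80 and 10.0 m at SD 100. The common slope falls midway, so it misses the Month 12 slope by half the gap:

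bias = (gap/2) × baseline imbalance

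At gap 0.2 this is 0.1 × 8.0 = 0.8 m, or 0.1 × 10.0 = 1.0 m. It favours 80 mg if the Month 12 slope is the steeper. At gap 0 it is zero, whatever the missingness.

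**Bias by simulation.** Month 12, 80 mg minus 5 mg, 300,000 per arm. Entries are the common-slope estimate minus the visit-specific estimate, over several missing-visit patterns and both baseline SDs.

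| Slope gap | By hand, moderate (SD 80 / 100) | Simulated, moderate | Simulated, strong |
|---|---|---|---|
| 0.1 | 0.4 / 0.5 m | 0.4–0.9 m | 0.9–2.0 m |
| 0.2 | 0.8 / 1.0 m | 0.8–1.8 m | 1.8–4.0 m |
| 0.3 | 1.2 / 1.5 m | 1.3–2.6 m | 2.8–5.8 m |

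With `BASE*avisitn` the bias is zero within simulation noise (about 0.4 m).

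**A second simulation** used baseline SD 85 m, residual SDs 55 and 60 m, correlation 0.6, Month 12 missing in 25/20/15% (5/20/80 mg), and odds of missing 2.2 times higher per SD lower baseline. Bias was 0.46, 0.96 and 1.46 m at the three gaps, and −0.04 m with the added term (Monte Carlo error about 0.16 m).

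**Precision, 143 per arm (SE in m, common slope against visit-specific).**

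| Slope gap | No missing data | Moderate | Strong | Second simulation |
|---|---|---|---|---|
| 0 | 7.06 v 7.06 | 7.66 v 7.66 | 7.73 v 7.74 | 7.74 v 7.74 |
| 0.1 | 7.09 v 7.07 (+0.3%) | 7.72 v 7.69 (+0.4%) | 7.77 v 7.75 (+0.3%) | 7.78 v 7.74 (+0.5%) |
| 0.2 | 7.15 v 7.07 (+1.1%) | 7.82 v 7.69 (+1.7%) | 7.88 v 7.76 (+1.5%) | 7.90 v 7.74 (+2.1%) |
| 0.3 | 7.25 v 7.07 (+2.5%) | 7.97 v 7.68 (+3.8%) | 8.03 v 7.75 (+3.6%) | 8.10 v 7.74 (+4.7%) |

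With no missing data there is no bias at any gap.

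**Type I error (two-sided, nominal 5%).** In the second simulation at gap 0.2, bias/SE = 0.96/7.90 = 0.12, and Φ(−1.96 + 0.12) + Φ(−1.96 − 0.12) gives 5.2%. At gap 0.3, 1.46/8.10 = 0.18 gives 5.4%. Under strong missingness the simulated rates were 7.6% (gap 0.2) and 9.9% (gap 0.3), against 5.1% and 6.4% with the added term, with simulation error of 0.6 to 0.8 points. The normal formula gives 7.0% (3.29/7.88 = 0.42) and 8.6% (4.45/8.03 = 0.55) for the same two cases.

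**The case against.** The strongest reply is that a common slope is a legitimate, simpler model and that nothing in the documents shows it to be wrong here. That stands. By the slope formula, growing spread in walk distance can offset a falling correlation. If total spread stays at 85 m and residual SDs are 55 and 60 m, the implied correlations are √(1 − (55/85)²) = 0.76 and √(1 − (60/85)²) = 0.71, a gap of only about 0.05. The hand formula then gives 0.025 × 8.0 = 0.2 m.

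The wording of Section 8.2 B also limits the point. A reader might infer that the SAP text itself imposes the common slope. It does not: it names baseline, treatment and strata, but no visit term, treatment-by-visit term or covariance structure. Only code offered as a sample does so.

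A reader might infer that differential missingness alone biases the contrast. It does not; at gap 0 there is neither bias nor precision loss.

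A reader might also take the DMC's mortality concern for 5 mg (Protocol Appendix 6, SAP Section 9) as evidence that low-baseline subjects in that arm lack Month 12 walks. The documents do not support this. The concern arose at 72 deaths across the whole trial and is not tied to Month 12 or to baseline 6MWD. The Protocol's 20% drop-out is not split by arm or baseline.

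Finally, prior treatment and etiology also lack visit interactions in the same code line. The same logic applies to them, but no calculation was made for them.

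What remains is that the restriction is unexplained, no section removes it, and lifting it costs essentially nothing.

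**Conclusion.** The point holds as a minor, conditional one. The sample code fits one baseline slope to both visits, and the SAP text does not ask for anything else. Harm needs two steps. If the true slopes differ, the Month 12 SE rises by up to about 5% for gaps up to 0.3. If baseline-related missingness also differs by arm, the contrast is biased by roughly 0.5 to 2 m under moderate assumptions (0.4 to 2.6 m over the whole moderate grid), against an SE of about 7.7 to 8 m. Biases of about 3 to 6 m need a gap of 0.2 to 0.3 together with 50% missing among low-baseline subjects in one arm. All slope gaps and arm-specific missing rates are assumptions.

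Only the 6MWD comparisons are affected. They are secondary and carry no multiplicity adjustment, and the mortality decision rule does not use them. It would be wrong to read the added term as a cure for missing walks generally: the bias vanishes in these checks because missingness was made to depend on baseline. Walks missing because of death, or for reasons beyond the observed data, remain an open question.

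**What to change.** Add `BASE*avisitn` to the MODEL statement in SAP Appendix 2.4. State in Section 8.2 B that the effect of baseline 6MWD is estimated separately at Months 6 and 12. Use the same model for the ITT, PP and figure outputs.

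The cost is one parameter and one sentence, with no new data. If the slopes are in fact equal, the SE is unchanged for practical purposes (7.73 m without the term, 7.74 m with it). The SAP keeps the study team blinded until final database lock, so the change can be prespecified if it is made before then.
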